## **9.0 Confidentiality, Privacy and Data Management**

See the Research Data Plan Review Form

## **10.0 Data and Safety Monitoring Plan**

### **10.1 Periodic evaluation of data**

We plan to perform an interim analysis of the data collected after every 30 patients enrolled in the study, until our sample size of 120 patients is achieved. We anticipate that patients receiving antagonists of the renin angiotensin aldosterone system will experience hypotension following the administration of propofol, although this is routine practice in anesthesiology without scientific literature to contraindicate practice. Our plan to treat hypotension with vasopressors is supported by the scientific literature(Mets, 2013), although we will modify our treatment plan accordingly if we deem that it is either causing hypertension or inadequate treatment of hypotension when it occurs.

### **10.2 Data that are reviewed**

Both propofol and methohexitol have a long record of safety in anesthesia practice. However, the investigators will monitor for new safety and adverse data of these drugs as presented by medical literature to ensure that our subjects remain safe throughout the conduct of this study. Our interim analysis, as described above, will be performed using hemodynamic data (blood pressure, heart rate) and vasopressor type and dosage, as obtained from the RedCap database.

### **10.3 Method of collection of safety information**

Any adverse effects believed to be related to the administration of study drug (as determined by anesthesiologist co-investigators in this study) will be recorded on a case report form and submitted to the PI of the study within 24 hours of occurrence.

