#### **7.4.5 Blinding of the Test Article**

The test drug will not be blinded

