##### **7.4.6.3 Preparation and Dispensing**

Refer to Anesthesia Protocol Sheet for Anesthesiologist for specific instructions on preparation and administration of study drugs. The study drugs will be prepared by one of the study anesthesiologists, and preparation and dose to be administered will subsequently be verified by another study anesthesiologist or

a study CRNA (if they are clinically available). Documentation of training by the checking anesthesiologist or certified registered nurse anesthetist (CRNA) will be required. The study team will provide a copy of the protocol and prepare a training document that summarizes the study and the checking anesthesiologist (or CRNA) responsibilities. A delegation log will be maintained to document this training. Only trained providers may act as the checking anesthesiologist for the research.

Anesthesia induction will be performed by one of the trained co-investigator anesthesiologists as described above.

The exact dose of propofol to be used for induction will be divided into two doses of identical volume, each half-dose placed in a sterile 60ml syringe by the administering anesthesiologist. The exact dose of methohexitol to be used for induction will be divided into two doses of identical volume, each half-dose placed in a sterile 60ml syringe by the administering anesthesiologist. This division of doses and placement into 60ml syringes is required to attain the infusion rate required by our study protocol by using the Medfusion 3500 pumps available at our institution. Both drugs will be administered via pre-established intravenous access by using Medfusion 3500 pumps at a pre-programmed rate of infusion during anesthetic induction.

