#### **10.5 Individuals reviewing the data**

The data will be reviewed by the PI and anesthesiologist co-investigators on a case-by-case basis to determine whether the adverse effect (if any) is related to administration of the study drug and whether this should influence the future conduct of the study.

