## 19.0 Adverse Event Reporting

### 19.1 Adverse Event Definitions

For drug studies, incorporate the following definitions into the below responses, as written:	
Adverse event	Any untoward medical occurrence associated with the use of the drug in humans, whether or not considered drug related
Adverse reaction	Any adverse event caused by a drug
Suspected adverse reaction	Any adverse event for which there is a reasonable possibility that the drug caused the adverse event. Suspected adverse reaction implies a lesser degree of certainty about causality than “adverse reaction”. 
 
Reasonable possibility. For the purpose of IND safety reporting, “reasonable possibility” means there is evidence to suggest a causal relationship between the drug and the adverse event.
 

Serious adverse event or Serious suspected adverse reaction	Serious adverse event or Serious suspected adverse reaction: An adverse event or suspected adverse reaction that in the view of either the investigator or sponsor, it results in any of the following outcomes: Death, a life-threatening adverse event, inpatient hospitalization or prolongation of existing hospitalization, a persistent or significant incapacity or substantial disruption of the ability to conduct normal life functions, or a congenital anomaly/birth defect. Important medical events that may not result in death, be life-threatening, or require hospitalization may be considered serious when, based upon appropriate medical judgment, they may jeopardize the patient or subject and may require

	medical or surgical intervention to prevent one of the outcomes listed in this definition.
Life-threatening adverse event or life-threatening suspected adverse reaction	An adverse event or suspected adverse reaction is considered “life-threatening” if, in the view of either the Investigator (i.e., the study site principal investigator) or Sponsor, its occurrence places the patient or research subject at immediate risk of death. It does not include an adverse event or suspected adverse reaction that had it occurred in a more severe form, might have caused death.

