## 19.2 Recording of Adverse Events

All adverse events (serious or non-serious) and abnormal test findings observed or reported to study team believed to be associated with the study drug(s) or device(s) will be followed until the event (or its sequelae) or the abnormal test finding resolves or stabilizes at a level acceptable to the investigator.

An abnormal test finding will be classified as an adverse event if one or more of the following criteria are met:

- The test finding is accompanied by clinical symptoms
- The test finding necessitates additional diagnostic evaluation(s) or medical/surgical intervention; including significant additional concomitant drug treatment or other therapy

**NOTE:** Simply repeating a test finding, in the absence of any of the other listed criteria, does not constitute an adverse event.

- The test finding leads to a change in study drug dosing or discontinuation of subject participation in the clinical research study
- The test finding is considered an adverse event by the investigator.

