## 19.3 Causality and Severity Assessments

The investigator will promptly review documented adverse events and abnormal test findings to determine 1) if the abnormal test finding should be classified as an adverse event; 2) if there is a reasonable possibility that the adverse event was caused by the study drug(s) or device(s); and 3) if the adverse event meets the criteria for a serious adverse event.

If the investigator’s final determination of causality is “unknown and of questionable relationship to the study drug(s) or device(s)”, the adverse event will be classified as associated with the use of the study drug(s) or device(s) for reporting purposes. If the investigator’s final determination of causality is “unknown but not related to the study drug(s) or device(s)”, this determination and the rationale for the determination will be documented in the respective subject’s case history.

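### Section 10.3 has unblinded co-investigators judge drug-relatedness before an adverse event reaches a case report form, contrary to sections 19.1, 19.3 and 20.1.2; non-hemodynamic events are the ones exposed

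*Combined protocol and SAP*

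**What the plan says.** Section 10.3 is the operative collection rule: "Any adverse effects believed to be related to the administration of study drug (as determined by anesthesiologist co-investigators in this study) will be recorded". The record meant is the case report form, which goes to the principal investigator within 24 hours. Section 7.4.5 states: "The test drug will not be blinded". Section 7.4.6.3 states: "Anesthesia induction will be performed by one of the trained co-investigator anesthesiologists". Under section 10.4 the case report forms are collected and analyzed after every 30 patients up to 120, and section 10.6 sets the same interval for cumulative review. Section 10.5 has the principal investigator and the co-investigators go through the data case by case "to determine whether the adverse effect (if any) is related to administration of the study drug".

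Other sections treat recording and causality as separate steps. Section 19.1 defines an adverse event as "Any untoward medical occurrence associated with the use of the drug in humans, whether or not considered drug related". Section 19.3 has the investigator assess causality on adverse events that are already documented. If the conclusion is that the cause is unknown but not the study drug, "this determination and the rationale for the determination will be documented" in the subject's case history. Section 20.1.2 has the principal investigator confirm that all adverse events are correctly entered in the forms, and a monitor check the entries against source documents. Neither duty carries a relatedness condition.

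Section 19.2 is headed as a recording section but gives a follow-up rule, with the qualifier "observed or reported to study team believed to be associated with the study drug(s) or device(s", and no general instruction on what to record.

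**The concern.** Followed as written, section 10.3 makes belief in a causal link the condition for completing a form. The judgement falls to people who have just given the drug and know which one it was. An event put down to intubation, sevoflurane, rocuronium, fentanyl or the patient's disease gives them no reason under 10.3 to fill one in.

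Two things are at stake. First, the periodic review may never see an unexpected pattern, because each event making up the pattern was individually explained away. Second, section 11.0 undertakes to stop the study if one drug appears to be causing significantly more harm than the other. That judgement needs event counts that do not depend on what staff expect of each drug. Expectations are stated in the plan: the section 1.1 hypothesis predicts more hypotension with propofol. Section 11.0 lists bronchospasm, vocal cord spasm and seizure under methohexitol but not under propofol. An identical event could therefore be judged differently in the two arms, in a direction that cannot be predicted.

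**Working it through.** The plan states no figure on this point, so the check is mainly a comparison of its rules.

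1. **What triggers a record.** Section 10.3: belief that the event is drug-related. Section 19.1: any untoward occurrence, regardless of attribution. Section 20.1.2: all adverse events entered. The first is narrower than the other two.

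2. **When causality is decided.** Section 10.3: before the form is completed. Section 19.3: after the event is documented, with unrelated as a possible finding. An event judged unrelated at the outset meets the 19.3 documentation rule only if something other than 10.3 put it on file.

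3. **What section 10.5 can add.** Its task is to decide "whether the adverse effect (if any) is related to administration of the study drug". If its input is the 10.3 forms, every event has already been answered yes by the same group. The review can overturn a yes but cannot recover a no, so it is circular.

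4. **Which data escape the filter.** Section 7.2.2 records systolic and diastolic pressure and heart rate every minute for 15 minutes in every patient. Vasopressor doses and refractory hypotension are secondary endpoints (section 1.3). Section 10.2 builds the interim analysis from hemodynamic and vasopressor data. None of this depends on opinion.

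5. **What remains exposed.** Non-hemodynamic events are not in the section 10.2 data. They reach the every-30-patient review mainly through the case report forms of section 10.4, that is, after the filter.

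6. **How attribution would act on a comparison (illustration).** Expected recorded events in an arm = n × r × a, where n is the number of patients, r the true event rate and a the probability that an event is believed drug-related. With equal n and r, the ratio of recorded counts is a₁/a₂, and the true rate cancels. Take n = 60 per arm (section 8.1) and assume r = 20% in both arms, so 60 × 0.20 = 12 true events each. The values of r and a are assumptions and are not in the documents.
   - a = 0.90 and 0.90: 10.8 v 10.8, ratio 1.0
   - a = 0.90 and 0.70: 10.8 v 8.4, ratio 1.29
   - a = 0.90 and 0.50: 10.8 v 6.0, ratio 1.8
   - a = 0.70 and 0.30: 8.4 v 3.6, ratio 2.33

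   Swapping the arms inverts each ratio. With r = 10% or 30% the counts change and the ratios do not. Equal attribution leaves the ratio at 1.0 but still loses the share 1 − a of events in both arms.

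**The case against.** The best defence is that section 10.3 is an expedited route and not the whole recording rule. It says that believed-related effects are recorded and sent within 24 hours; it does not say that others go unrecorded. On that reading the coordinator enters all events under 20.1.2, the investigator judges causality under 19.3, and related events also travel quickly under 10.3. This has force. A reader might infer that unrelated events are never recorded, or that the sections cannot all be obeyed, and the documents support neither inference. What they show is a conflict in wording that staff must resolve for themselves. The section whose title covers collection of safety information gives them the narrow rule, and section 19.2 supplies no broad one to set against it. The qualifier in 19.2 limits follow-up; it should not be read as a second filter on recording.

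A reader might also infer that the reviewers have no unfiltered safety data. That is not so: the main foreseeable harm, hypotension, is captured without attribution. Arrhythmia around induction and an unanticipated difficult airway are removal criteria in section 3.3.1 whatever their cause, so they should leave some trace even without an adverse event form.

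Finally, no comparison of adverse events by arm is specified. Section 8.3 lists none and section 10.7 marks statistical tests as not applicable. This stands: the plan contains no by-arm safety analysis that could be called biased. The point applies to any comparison drawn from the forms, including the comparative judgement that section 11.0 promises.

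**Conclusion.** The point holds in limited form. Section 10.3 conflicts with sections 19.1, 19.3 and 20.1.2, and if it governs what is recorded, the relatedness review in 10.5 is circular. The exposure is confined to non-hemodynamic events and to judgements that rest on the case report forms. The primary endpoint and the hemodynamic secondary endpoints are not affected.

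The size cannot be estimated. The ratios of 1.0 to 2.33 above restate assumed attribution probabilities. They show the mechanism, and that it can run in either direction; they do not forecast a bias in this trial. The conclusion assumes that staff would take 10.3 at its word. If they already follow 20.1.2 and enter everything, the consequence in practice is small and only the text needs correcting. The change should be made because it is cheap and because an event not written down at the time may not be recoverable later.

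**What to change.** Reword section 10.3 to agree with 19.1, 19.3 and 20.1.2: every adverse event as defined in 19.1, from the start of the pre-induction drugs to the end of study participation under section 7.3, is recorded on the case report form whatever its presumed cause. Add the same recording sentence to section 19.2, leaving its follow-up rule distinct. Enter relatedness afterwards, as a separate field under 19.3. Keep the 24-hour submission to the principal investigator for events believed related.

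In the 10.5 and 10.6 reviews and in the final report, tabulate all recorded events by randomized arm, with related events shown as a subset. The all-event counts then do not depend on attribution. The related subset still will, because the assessors remain unblinded; an assessor unaware of the arm would help where one is available.

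The cost is a wording amendment, one extra field on the form and a few more entries per patient over a short window. No treatment or procedure changes.

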### **10.4 Frequency of data collection**

Due to the established safety of the 2 study drugs compared to the number of patients being studied, case report forms will be collected and analyzed after every 30 patients enrolled in the study, until our sample size of 120 patients is achieved.

#### **10.5 Individuals reviewing the data**

The data will be reviewed by the PI and anesthesiologist co-investigators on a case-by-case basis to determine whether the adverse effect (if any) is related to administration of the study drug and whether this should influence the future conduct of the study.

#### **10.6 Frequency of review of cumulative data**

After every 30 patients enrolled in the study, until our sample size of 120 patients is achieved.

#### **10.7 Statistical tests**

Not applicable, due to the established safety of the study drugs compared to the study population size.

#### **10.8 Suspension of research**

Not applicable, due to the established safety of the study drugs.

### **11.0 Risks**

The research requires the establishment of a second intravenous line following anesthetic induction. The use of an additional intravenous line is common anesthetic practice, although (as with any invasive procedure) there is the risk of bleeding, infection at the venipuncture site and infiltration of the intravenous catheter with the infusion of medications or fluids. In this study, the line will be used to draw blood samples, but following termination of the study protocol it will be used for the administration of standard fluids and drugs required for anesthetic care.

While there is currently no evidence to suggest that either randomization arm is harmful compared to the other, there is the risk that patients will be randomized to receive an induction drug that may potentially cause more hypotension compared to the other. We will perform interim analysis of our data and stop the study should we have reason to believe that one medication is causing significant harm compared to the other. Patients will be randomized to receive either propofol or methohexitol which both have the potential to cause hypotension.

Risks of propofol:

>10% incidence: low blood pressure (3%-26%), Injection site burning, stinging, or pain (18%), stop breathing for 30-60 seconds (adults 24%)

1% to 10% incidence: abnormal heart rhythm (1% to 3%), slow or fast heart rate (1% to 3%), cardiac output (volume of blood pumped by the heart per minute) decreased (1% to 3%);

Risks of methohexitol (frequency not defined but these complications are considered very rare since methohexitol is considered standard of care):

Sudden stop in blood circulation due to the failure of the heart, low blood pressure, shutdown of arteries and veins in the arms and legs, fast heart rate, agitation coming out of general anesthesia, headache, anxiety, restlessness, seizures, convulsion, injection site pain, abdominal pain, nausea or vomiting, blood clot in your leg that blocks one or more of your veins, breathing problems (stop breathing, bronchospasm, cough, labored breathing, hiccups, spasm of the vocal cords making it difficult to speak or breath, inadequate breathing).

One of three trained anesthesiologists will be administering each of these induction drugs, and has the expertise to anticipate and effectively treat each of these potential complications.

There is a possible risk of loss of confidentiality of health information.

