## 2.0 Background

### 2.1 Scientific Background and Gaps

Induction of anesthesia in patients treated preoperatively with ACEI or ARB is often associated with significant hypotension. (Rosenman et al., 2008) (Bertrand et al., 2001) One stated reason for this hypotension is the fact that antagonists of the renin-angiotensin system may reset baroreceptor function inhibiting compensatory heart rate increases in the face of hypotension. (Giudicelli et al., 1985) The intravenous induction agents, methohexitol and propofol have opposing effects on this baroreceptor function; (JW, 2011) methohexitol administration increases baroreceptor sensitivity with a resultant increase in heart rate, (Carter et al., 1986) while propofol decreases baroreceptor sensitivity in the face of induced hypotension. (Cullen et al., 1987; Ebert et al., 1992) Consistent with this, when induction of anesthesia in ASA Physical Class 1 and 2 patients was compared, methohexitol was associated with better maintenance of heart rate and blood pressure than propofol induction.(Gold et al., 1987; Price et al., 1992) Given the significant hypotension often encountered with the use of Propofol for induction in patients on ACEI or ARB therapy(Bertrand et al., 2001; Mets, 2013; Nielson et al., 2014) and the fact that there are now increasing concerns around the use of the more cardiostable induction agent etomidate,(Komatsu et al., 2013) there is a need to establish the utility of other cardiostable induction agents for use in the increasing number of patients presenting on antagonists of the renin-angiotensin system.

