## 8.2 Sample size determination

The primary outcome of this two-arm trial is the proportion of subjects that have at least one hypotension episode within 15 minutes of administration of the randomized treatment medication. A hypotension episode is defined as having a drop in systolic blood pressure  $>30\%$  from baseline and/or having systolic blood pressure  $<85$  mmHg. Eyraud et al found 42 out of 51 subjects (0.82) had at least one hypotension episode using propofol (Eyraud et al., 1999). We expect our propofol proportion to be slightly higher due to our definition of a hypotension episode and our patient population. Further, we believe an absolute reduction of 0.30 in the proportion of subjects having at least one hypotension episode in the methohexitol group compared to the propofol group is clinically important. Although the randomization will be stratified by two factors (gender and drug type), to provide a conservative sample size estimate these factors were not taken into consideration for the power analysis because the correlation of these stratification covariates with the outcome would simply increase the precision, and hence, increase the power.

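### Section 11 gives hypotension risks (3%-26% with propofol, very rare with methohexitol) that do not agree with the rates on which Section 8.2 sizes the trial

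*Combined protocol and SAP*

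**What the plan says.** Section 11.0 (Risks) lists, for propofol, ">10% incidence: low blood pressure (3%-26" per cent). It does not say what counts as low blood pressure, in which patients, or where the range comes from.

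For methohexitol the same section introduces its list with "frequency not defined but these complications are considered very rare since methohexitol is considered standard of care". The list begins "Sudden stop in blood circulation due to the failure of the heart, low blood pressure", so hypotension falls under that description.

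Section 8.2 (Sample size determination) takes its propofol rate from a cited study, which "found 42 out of 51 subjects (0.82) had at least one hypotension episode using propofol". It then adds: "We expect our propofol proportion to be slightly higher due to our definition of a hypotension episode and our patient population". It calls a 0.30 absolute reduction with methohexitol clinically important and states no methohexitol rate. Section 8.1 gives 47 per group for 90% power and 120 in total after allowing for 20% drop-out.

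Section 1.2 makes hypotension the primary endpoint: a 30% fall in systolic pressure from baseline, a systolic pressure under 85 mmHg, or both. One episode in the 15 minutes after induction is enough.

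**The concern.** The two sections describe the same event in the same participants and give very different pictures. By Section 11, hypotension affects at most about a quarter of propofol subjects and almost no methohexitol subjects. By Section 8.2, it affects more than four in five propofol subjects, and the trial is sized on about half of methohexitol subjects.

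Section 8.2 attributes its higher expectation to the definition and the population. The protocol therefore recognises that both matter to the rate, yet Section 11 adjusts for neither and does not mark its figures as general.

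Hypotension is the primary-endpoint event, and Section 12.1 promises subjects no benefit. Section 11 is the protocol's statement of the risk they accept, so its account of this event should match what the investigators anticipate.

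**Working it through.** **Inputs.** Section 11: propofol 3% to 26%; methohexitol very rare, with no number. Section 8.2: propofol reference 42/51, with slightly more expected here; reduction of interest 0.30. Section 8.1: 47 per group, 90% power, two-sided chi-square test at 0.05; 20% drop-out; 60 per arm.

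**1. Which rates lie behind the plan's 47 per group?** With pooled variance under the null and no continuity correction,

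n = [1.960 × √(2p̄(1 − p̄)) + 1.2816 × √(p₁(1 − p₁) + p₂(1 − p₂))]² / 0.30²

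- 0.85 v 0.55 (p̄ = 0.70): [1.960 × √0.42 + 1.2816 × √0.375]² / 0.09 = 46.9, so 47 per group. This matches, with power 0.9005 at 47.
- 0.82 v 0.52 (p̄ = 0.67): [1.960 × √0.4422 + 1.2816 × √0.3972]² / 0.09 = 49.5, so 50 per group, with power 0.884 at 47. The unpooled formula gives 47 for this pair.
- Drop-out: 47/0.80 = 58.75, so 59 per arm or 118 in total, consistent with the rounded 120.

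The sizing therefore fits propofol at 0.82 to 0.85 and methohexitol at 0.52 to 0.55. The 0.85 is inferred; the protocol does not state it.

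**2. Propofol: Section 8.2 against Section 11.**

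- 42/51 = 0.8235.
- Against the top of the range: 0.82/0.26 = 3.2, or 0.85/0.26 = 3.3.
- The exact 95% interval for 42/51 is 0.69 to 0.92. Its lower limit is still 0.69/0.26 = 2.7 times the top of the range, so sampling error in a study of 51 does not explain the gap.
- In 60 propofol subjects: 0.82 × 60 = 49 with hypotension, against 0.03 × 60 = 2 to 0.26 × 60 = 16 by Section 11.

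**3. Methohexitol.**

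- Design assumption: 0.82 − 0.30 = 0.52, or 0.85 − 0.30 = 0.55. In 60 subjects, 0.52 × 60 = 31.
- Section 11 gives no frequency, so no ratio can be formed.
- For hypotension to be very rare with methohexitol while propofol is above 0.82, the reduction would have to be about 0.8. The trial is sized for 0.30.

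**4. Effect on the statistics.** The Section 11 rates enter no formula in Section 8, so sample size, power and analyses stay as they are.

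**The case against.** The strongest reply is that the two propofol figures may measure different things. The 3%-26% has no stated definition or population and may well hold for general use. The 0.82 counts patients with one or more episodes in a particular study. That stands. A reader might infer that the Section 11 range is itself wrong several-fold, but the documents do not show this. They show a figure that is unlabelled and does not fit this population and endpoint.

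Other stronger readings also go too far:

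- **That the plan forecasts 52% with methohexitol.** Section 8.2 calls 0.30 clinically important and gives no methohexitol rate. The 0.52 to 0.55 is what the sizing implies.
- **That the reviews after every 30 patients would be misled, or would look alarming in both arms.** Section 11 frames harm as one drug against the other, and no section tells the team to compare either arm with 3%-26%. Section 8.2 supplies another rate, and Section 10.1 already anticipates hypotension after propofol in these patients.
- **That the statement "there is currently no evidence to suggest that either randomization arm is harmful compared to the other" contradicts Section 2.1 and must go.** The same sentence goes on to disclose that one drug may cause more hypotension. The Section 2.1 evidence, that "methohexitol was associated with better maintenance of heart rate and blood pressure than propofol induction", comes from ASA class 1 and 2 patients, whereas this trial enrols class II or III patients on ACEI or ARB.
- **That subjects are told the wrong risk.** The consent pages are not among the material reviewed, so this cannot be judged.

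It is also fair to object that printing about half for methohexitol could turn an untested design value into a quoted drug risk. That is a reason to label the value as an assumption. It is no reason to leave low blood pressure under very rare.

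**Conclusion.** The inconsistency is real and should be corrected. For propofol, the rate the trial is planned on is at least about 3 times the top of the range given as the risk. For methohexitol, an event described as very rare is one that the sizing places in about half of subjects. That second contrast rests on the 0.30 reduction being the true effect and is qualitative only.

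The propofol comparison assumes that the 42/51 reference carries over to this trial, as Section 8.2 says it does with a slight increase. It does not depend on 3%-26% being wrong for general use. The consequence is limited to how the risk of the primary-endpoint event is described to participants and to those who review the protocol.

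**What to change.** In Section 11.0:

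1. Label 3%-26% as a general-use figure and give its source and, if known, its definition of low blood pressure.
2. Add that, under the protocol's definition and in patients on ACEI or ARB, hypotension is anticipated in more than 80% of propofol subjects, with a reference to Section 8.2.
3. Remove low blood pressure from the methohexitol complications described as very rare. State that it is expected to be common with methohexitol too: the trial is sized on roughly half of subjects, which is a design assumption and not an observed rate.
4. Check that the consent wording agrees with the revised section, and change it only if it does not.

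The sentence on lack of evidence of comparative harm can stay. The cost is a wording amendment and the disclosure of a less favourable figure. No sample size, power calculation, analysis or study procedure changes.
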